# 7.5.6 Analysis of Overall Survival

The primary objectives of the study are to compare the overall survival between treatment groups in randomized subjects with PD-L1 CPS  $\geq$  20 and in all randomized subjects.

Overall survival will be compared between the treatment groups at the interim and final analyses, using a stratified log-rank test. The stratification factors will be tumor cell PD-L1 status, HPV p-16 status and prior chemotherapy status. Graphic procedure (Figure 7.5.6-1:) and an O'Brien and Fleming  $\alpha$ -spending function will be employed to determine the nominal significance levels for the interim and final analyses. Details of this sequentially rejective procedure will be provided in Appendix 4.

Figure 7.5.6-1: Testing Hierarchy for the Endpoints

The stratified hazard ratio between the treatment groups will be presented along with  $100*(1-\alpha)\%$  CI (adjusted for interim). In addition, two-sided p-value will also be reported for the analysis of OS.

OS will be estimated using the KM techniques. A two-sided 95% CI for median OS in each treatment group will be computed via the log-log transformation method. OS rates at fixed time points (e.g. 6 months, depending on the minimum follow-up) will be presented along with their associated 95% CIs. These estimates will be derived from the Kaplan Meier estimate and corresponding CIs

will be derived based on Greenwood formula for variance derivation and on log-log transformation applied on the survivor function.

The status of subjects who are censored in the OS KM analysis will be tabulated for each treatment group using the following categories:

- On-study (on-treatment, in follow-up)
- Off-study (lost to follow-up, withdraw consent, never treated)

A by-subject listing will be presented including treatment group, first and last dose date, whether the subject died, and if censored, the reason, event/censored date and OS duration.

# 7.5.7 Supportive Analyses of Overall Survival

The following OS sensitivity analyses will be conducted in all randomized subjects:

- 1) Delayed effect of immunotherapy interventions may cause a late separation in the OS KM curves and non-proportional hazards. OS will be compared between treatment groups via two-sided stratified weighted log-rank test among subjects. The two-sided stratified weighted log-rank p-value will be reported using G (rho = 0, gamma = 1) weights, in the terminology of Fleming and Harrington.
  - The Fleming Harrington test can be unstable, so it is possible, though uncommon, that the p-value for this trial will not be estimable.
  - Further, Max-combo testing and estimating procedure might be applied.
- 2) A multivariate Cox regression model will be used in order to estimate the treatment effect after adjustment for possible imbalances in known or potential prognostic factors. The factors used in the randomization, which, by definition, will be balanced across treatment groups, will still be included in the model as stratification factors. However, all additional factors will be incorporated as covariates. The additional factors, which are all measured at baseline, will include, but not limited to:
  - a. ECOG PS  $(0, \ge 1)$
  - b. SEX (Male, Female)
  - c. AGE

The level of the covariate normally associated with the worst prognosis will be coded as the reference level. The hazard ratio associated with treatment and with each of the baseline covariates will be presented along with associated  $100*(1-\alpha)\%$  CIs (adjusted for interim).

- 3) OS using stratification factors as obtained from the baseline CRF pages (instead of IRT). The hazard ratio associated with treatment will be presented along with the associated two-sided 100\*(1- α)% CI (adjusted for interim). This analysis will be performed only if at least one stratification variable/factor at randomization (as per IRT) and baseline are not concordant for at least 10% of the randomized subjects.
- 4) OS using an un-stratified log rank test. The hazard ratio associated with treatment will be presented along with the associated two-sided  $100*(1-\alpha)\%$  CIs (adjusted for interim).
- 5) OS for subjects with no relevant protocol deviations. This analysis will be conducted only if there are more than 10% subjects with relevant protocol deviations. The hazard ratio

associated with treatment will be presented along with the associated two-sided  $100*(1-\alpha)\%$  CIs (adjusted for interim).

- 6) OS will be compared between treatment groups using a two-sided stratified log-rank test in the All Treated Subjects population, using arm as treated. This analysis will be performed only if the proportion of randomized but never treated subjects exceeds 10%.
- 7) To examine the assumption of proportional hazards in the Cox regression model, in addition to treatment, a time-dependent variable defined by treatment by time interaction will be added into the model. A two-sided Wald Chi-square p-value of less than 0.1 may indicate a potential nonconstant treatment effect. In that case, additional exploratory analyses may be performed.

# 7.5.8 Subset Analyses of Overall Survival

The influence of baseline and demographic characteristics on the treatment effect among all randomized subjects will be explored via exploratory subset analyses. The median OS based on KM product-limit method along with two-sided 95% CIs will be produced for the following subgroups:

- Age categorization (<65 vs.>=65 vs. ≥65-<75 vs >75)
- Sex (Male vs. Female)
- Race (White, Black, Asian, Others)
- Region (North America vs. EU vs. Asia vs. ROW)
- ECOG performance status $(0, \ge 1)$
- Disease stage at initial diagnosis (Stage I, Stage II, Stage III, Stage IVA, Stage IVB, Stage IVC)
- Disease stage at study entry (locally recurrent, locally recurrent and metastatic, metastatic)
- Time from initial disease diagnosis to randomization (<1, 1-<2, 2-<3,3-<4, 4<-5, >=5 year)
- Site of primary tumor (Oral cavity, Oropharynx, Hypopharynx, Larynx)
- Tobacco use (Never, Former, Current, Unknown)
- Alcohol use
- Prior radiotherapy (yes/no)
- Prior surgery (yes/no)
- Prior systemic cancer therapy (yes/no)
- Prior platinum-based chemotherapy (yes/no)
- HPV status per IRT

A forest plot of the OS hazard ratios (along with the 95% CIs) will be produced for each level of the subgroups listed above.

An analysis will be conducted if the number of subjects in the subgroup category is more than 10.

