3 INVESTIGATIONAL PLAN

3.1 Study Design and Duration

Protocol CA209651 is a randomized open-label, Phase 3 trial in subjects ≥ 18 years old with untreated metastatic or recurrent SCCHN that is not amenable to curative therapy, evaluating nivolumab + ipilimumab versus the EXTREME regimen (cetuximab + cisplatin/carboplatin + fluorouracil) as a first-line treatment.

HPV p-16 status and tumor cell PD-L1 status (expressing or non-expressing/non-evaluable) test results will be needed prior to randomization. Subjects will undergo screening evaluations to determine eligibility prior to randomization.

The dose and treatment schedules for each arm are as follows:

- Arm A: Nivolumab + Ipilimumab Arm:
 - Nivolumab 3 mg/kg IV every 2 weeks + Ipilimumab 1 mg/kg IV every 6 weeks until progression, unacceptable toxicity, or a maximum of 24 months from first study treatment.
- Arm B: EXTREME regimen Arm:
 - Cetuximab 400 mg/m² IV for the initial dose only, then 250 mg/m² weekly + cisplatin (100 mg/m²) or carboplatin (AUC of 5 mg per milliliter per minute) on Day 1 and fluorouracil (1000 mg/m² per day for 4 days) every 3 weeks for maximum of 6 cycles followed by maintenance cetuximab at 250 mg/m² weekly (or every 2 weeks, per local prescribing information) until disease progression or unacceptable toxicity; the choice of cisplatin or carboplatin is at the discretion of the investigator.

Approximately 930 subjects will be randomized to the two treatment arms in a 1:1 ratio and stratified by the following factors:

- Tumor cell PD-L1 status (expressing [$\geq 1\%$] vs non-expressing [$< 1\%$] or non-evaluable). Up to 10% of randomized subjects per cohort can be included into the study as “non-evaluable.” After this point, subjects with non-evaluable results will not be permitted to be randomized; the site would need to submit an additional tumor tissue for testing with either a result of “expressing” or non-expressing” in order to randomize the subject.
- HPV p-16 status (oropharyngeal HPV p-16 positive vs oropharyngeal HPV p-16 negative or non-oropharyngeal). Oropharyngeal CA sites defined in [Appendix 5](#).
- Prior chemotherapy (adjuvant/neoadjuvant/multimodal treatment) status (Yes/No)

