3.3.1 Inclusion Criteria

1. Signed Written Informed Consent

- a) Participants must have signed and dated an IRB/IEC approved written informed consent form in accordance with regulatory and institutional guidelines. This must be obtained before the performance of any protocol related procedures that are not part of normal subject care.
- b) Participants must be willing and able to comply with scheduled visits, treatment schedule, and laboratory testing.

2. Target Population

- a) Histologically confirmed head and neck squamous cell carcinoma (SCCHN), from any of the following primary sites only: oral cavity, oropharynx, hypopharynx and larynx.
- b) Must have metastatic or recurrent disease that is not amenable to therapy with curative intent (surgery or radiation therapy with or without chemotherapy). Participants that refuse potentially curative salvage surgery for recurrent disease are ineligible.
- c) No prior treatment with systemic anti-cancer therapy for SCCHN, unless under all of the following conditions:
 - i) Prior chemotherapy was given as adjuvant or neoadjuvant chemotherapy, or part of multimodal (chemo, radiation) treatment for locally advanced disease
 - ii) These treatments must have been completed > 6 months prior to enrollment
 - iii) There is no evidence of disease progression for at least 6 months after completion of systemic treatment.
 - iv) Participants having progression after 2 cycles of induction chemotherapy are excluded.
- d) ECOG Performance Status of 0–1. (See [Appendix 1](#)).
- e) Measurable disease by CT or MRI per RECIST 1.1 criteria (see [Appendix 3](#)); radiographic tumor assessment performed within 28 days prior to first dose.
 - i) Target lesions may be located in a previously irradiated field if there is documented (radiographic) disease progression in that site after the completion of radiation therapy.
- f) Documentation of HPV p-16 status is required for SCCHN tumor of the oropharynx. See [Section 5.6.8](#) for additional guidance. Note: If results are not available, then a sample (tissue on microscopic slides, tissue block or a fresh tissue biopsy in formalin) should be sent to the central laboratory for analysis.
- g) Documentation of tumor cell PD-L1 status by IHC performed by the central lab prior to randomization.

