APPENDIX 5 HEAD AND NECK SQUAMOUS CELL CARCINOMAS CLASSIFIED AS FOLLOWS:

- oral cavity:
 - anterior two thirds of the tongue
 - tongue unspecified,
 - lip
 - gum
 - floor of the mouth
 - hard palate
 - palate unspecified
 - other oral cavity—including buccal mucosa and retromolar area
 - oral cavity unspecified

- oropharynx:
 - base of the tongue
 - soft palate
 - tonsil
 - uvula
 - other parts of the oropharynx
 - Waldeyer’s ring
 - oropharynx unspecified

- larynx:
 - glottis
 - supraglottis
 - subglottis
 - other and unspecified larynx subsites
 - Hypopharynx cases are classified as belonging to the larynx, including pyriform sinus

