#### 7.3.2 Demographics and Other Baseline Disease Characteristics

The following demographic and baseline disease characteristics will be summarized and listed by treatment group as randomized:

- Age (continuous)
- Age categorization ( $< 65, \ge 65 \text{ and } < 75, \ge 75 \text{ and } < 85, \ge 85, \ge 75, \ge 65$ )
- Sex (Male vs. Female)
- Race (White, Black or African American, Asian, Other)
- Ethnicity (Hispanic/Latino and Not Hispanic/Latino)
- Region (North America, EU, Asia, Rest of World)
- Country by geographic region
- Baseline ECOG performance status
- Tobacco use (Never, Former, Current, Unknown)
- Alcohol use
- Disease stage at study entry (locally recurrent, locally recurrent and metastatic, metastatic)
- Disease stage at initial diagnosis (stage I, II, III, IVA, IVB, IVC)
- TNM Classification at initial diagnosis
- Time from initial disease diagnosis to randomization (< 1 year,  $\geq$  1 year)
- Sites of primary tumor per investigator
- Subsites of diseases per investigator
- Sites of diseases (all lesions) per BICR
- Number of disease sites per subject (all lesions) per BICR
- Number of target lesions, non-target lesions and disease sites at baseline as per BICR
- Tumor burden: sum of the diameters of target lesions at baseline per BICR

- Tumor burden: sum of the diameters of target lesions at baseline per investigator
- HPV p-16 status per CRF
- Tumor cell PD-L1 proportion score (TPS) per CRF
- PD-L1 CPS
- CNS metastasis

Summary table (cross-tabulation) by treatment group for stratification factor will be provided to show any discrepancies between what was reported through IRT vs. CRF at baseline. This summary will be performed based on all randomized subjects.

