#### 7.6.16 Adverse Events by Subgroup

Overall summary of any AEs and drug-related AEs by worst CTC grade (any grade, grade 3-4, grade 5) presented by SOC/PT and for each treatment group for the following subgroups:

- Sex (Male vs. Female)
- Race
- Age  $(< 65 \text{ vs. } 65 < 75 \text{ vs. } 75 < 85 \text{ vs. } \ge 85 \text{ vs. } \ge 75 \text{ vs. } \ge 65)$
- Region (North America vs. EU vs. Asia vs. ROW)
- Prior chemotherapy status (Yes/No)

These analyses will be conducted using the 30-day safety window only.

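### The oldest age band in the OS subgroup analysis starts above 75, so participants aged exactly 75 are in neither fine band and the band does not match the rest of the SAP

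*SAP*

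**What the plan says.** **Age.** SAP 7.5.8 plans a median OS with 95% CI and a forest-plot hazard ratio for each level of a list of subgroups in all randomized subjects. It labels the whole set exploratory. The age entry is "Age categorization (<65 vs.>=65 vs. ≥65-<75 vs >75". SAP 7.3.2 (baseline characteristics) and SAP 7.6.16 (adverse events by subgroup) also split age at 65 and 75, but there the upper groups begin at 75 inclusive: 75 to under 85, 85 and over, and 75 and over.

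**Primary site.** The same list in SAP 7.5.8 has "Site of primary tumor (Oral cavity, Oropharynx, Hypopharynx, Larynx" as four levels. Protocol Section 3.3.1, criterion 2a, admits tumors "from any of the following primary sites only: oral cavity, oropharynx, hypopharynx and larynx", which also keeps hypopharynx and larynx apart. Protocol Appendix 5 has three headings (oral cavity, oropharynx, larynx) and, under the last, the line "Hypopharynx cases are classified as belonging to the larynx, including pyriform sinus". SAP 7.3.2 lists "Sites of primary tumor per investigator" and, separately, subsites, also per investigator. SAP 7.5.8 does not say which classification feeds the site subgroup.

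**The concern.** The age levels in SAP 7.5.8 are analysis rules that a programmer would code as written. Coded literally, the oldest OS subgroup leaves out everyone aged 75. The three finer levels no longer add up to all participants, and the oldest row of the OS forest plot describes a different population from the oldest row of the baseline and safety tables. Readers use these rows to judge whether the effect holds in older participants. A mismatch found after unblinding would mean regrouping the data post hoc, which can look data-driven.

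The site entry raises a smaller question of the same kind. Two classifications of hypopharynx exist in the documents, and the SAP does not name the one that defines the subgroup.

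**Working it through.** There is no power, alpha or event figure to reproduce here. The check is whether the levels cover every age once and agree across sections.

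**Step 1. Coverage of the age bands.** Every whole age from 18 to 100 was tested against each set of bands.

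| Source | Fine bands | Ages in no fine band |
|---|---|---|
| SAP 7.5.8 as written | <65; >=65 to <75; >75 | 75 only |
| SAP 7.3.2 | <65; >=65 to <75; >=75 to <85; >=85 | none |
| SAP 7.5.8 with >=75 | <65; >=65 to <75; >=75 | none, and no age counted twice |

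Under 7.5.8 as written, age 75 satisfies only the broad >=65 level. Hence the number aged >=65, minus the number in >=65 to <75, minus the number in >75, equals the number aged exactly 75. That remainder would be visible in the output.

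**Step 2. How many participants.** The planned sample is 930 (SAP 2.1). The documents give no age distribution, so the share aged exactly 75 is an assumption, taken as 0.5% to 2%.

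- 930 × 0.005 = 4.65, about 5
- 930 × 0.01 = 9.3, about 9
- 930 × 0.02 = 18.6, about 19

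**Step 3. The site classifications side by side.**

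| Place | Treatment of hypopharynx |
|---|---|
| Protocol 3.3.1, criterion 2a | separate from larynx |
| SAP 7.2, eligibility deviations | separate from larynx |
| SAP 7.5.8, OS subgroup | separate from larynx |
| Protocol Appendix 5 | under larynx |

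The protocol uses Appendix 5 for one purpose. In the Synopsis and in Sections 3.1 and 4.4 it is cited to define oropharyngeal sites for the HPV p-16 stratification factor: "Oropharyngeal CA sites defined in [Appendix 5". For that purpose the hypopharynx line has no effect, because hypopharynx and larynx are both non-oropharyngeal and fall in the same stratum level.

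**The case against.** The strongest reply on age is that this is a typing slip with an obvious intent. SAP 7.3.2 and 7.6.16 show the intended cut, and the time-since-diagnosis entry in the same list also has a misplaced inequality sign. A greater-or-equal sign could also have been lost when the PDF was read, although both forms of that sign survive elsewhere in the same line. The analyses are exploratory and no decision rests on them. All of this stands, and it makes the point minor. It does not make the rule correct as written.

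Three stronger readings are tempting, and the documents do not support them.

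- A reader might infer that participants are put in the wrong age group. They are not: those aged 75 are omitted from the fine bands and still count in >=65.
- A reader might infer that a known, large share of the oldest subgroup is lost. That share needs two assumptions, the proportion aged exactly 75 and the proportion aged 75 or over. Taking 0.5% and 8% gives 0.5/8, about 6%; taking 2% and 5% gives 2/5 = 40%. A range that wide says nothing useful, and nothing in the documents shows that 75 is an especially common age.
- A reader might infer from Appendix 5 that the hypopharynx subgroup will be empty and the larynx subgroup mixed. That would follow only if sites recorded primary tumor by Appendix 5. No section tells them to. The protocol cites the appendix only for oropharyngeal sites, and the SAP takes site and subsite per investigator. The Appendix 5 title is general and its hypopharynx line carries no stated limit, so a conflict remains to be reconciled, but misclassification is not shown.

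**Conclusion.** The age point holds. As written, SAP 7.5.8 leaves participants aged exactly 75 out of both fine bands, and its oldest OS subgroup does not match the 75-and-over group in SAP 7.3.2 and 7.6.16. The size is about 5 to 19 of 930 participants, on the assumption that 0.5% to 2% are aged exactly 75 and that age is analyzed in whole years, a derivation the SAP does not state. The effect is confined to exploratory subgroup displays; the primary tests, alpha, power and stratification do not change.

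The site point holds only as an unreconciled difference between Appendix 5 and the rest of the plan, with no demonstrated effect on any estimate. Both are minor corrections worth making before database lock.

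**What to change.** 1. In SAP 7.5.8, change >75 to >=75. The levels <65, >=65 to <75 and >=75 then cover every age exactly once and agree with SAP 7.3.2 and 7.6.16.
2. Add one sentence to SAP 7.5.8 stating that the primary-site subgroup uses the investigator-recorded four-site classification, checked against the recorded subsite. SAP 7.3.2 already plans to summarize the subsites, so no new data are needed.

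The cost is one symbol, one sentence and a derivation check in the SAP. No protocol revision is needed. Rewriting Appendix 5 would bring in the review steps of Protocol Section 9.1.1 and would not change site data already recorded.

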#### 7.5.9 Current Status of PFS and OS Follow-up

The extent of follow-up for survival, defined as the time between randomization date and last known alive date (for subjects who are alive) or death date (for subjects who died), will be summarized descriptively (median, min, max, etc.) in months for all randomized subjects.

The currentness of follow-up for survival, defined as the time between last OS contact (i.e., last known alive date or death date) and cutoff date (defined by last patient last visit date), will be summarized in months for all randomized subjects. Subjects who died and subjects with last known alive date on or after data cut-off date will have zero value for currentness of follow-up.

Minimum follow-up for OS, defined as the time from cutoff date to last subject's randomization date, will be summarized in months for all randomized subjects.

Time from last evaluable tumor assessment to cutoff date in months will be summarized by treatment group and overall for all randomized subjects. Subjects who have a PFS event will be considered as current for this analysis. The secondary definition of PFS will be used for this summary.

In addition, time to treatment discontinuation will be summarized and presented by treatment group using a Kaplan-Meier curve whereby the last dose date will be the event date for those subjects who are off study therapy. Median duration of study therapy and associated 95% CI will be provided. Subjects who are still on study therapy will be censored on their last dose date.

A by-subject listing will also be produced to accompany the subject time from last evaluable tumor assessment.

# 7.5.10 Interim Analyses of Overall Survival

An independent statistician external to BMS will perform the analyses. In addition to the formal planned interim analysis for OS, the Data Monitoring Committee (DMC) will have access to periodic un-blinded interim reports of efficacy and safety to allow a risk/benefit assessment. Details are included in the DMC charter.

A formal interim analysis for superiority of OS will be performed after approximately 593 OS events (80% of 741 required) have occurred on all randomized subjects, or all randomized subjects have been followed up for at least 12 months, whichever is later. Both primary endpoints will be tested at interim using the group sequential test procedure with initial overall alpha = 0.025 for each. The overall alpha will be updated following graphical procedure (Figure 7.5.6-1:). The stopping boundaries for the interim and final analyses will be determined by the O'Brien and Fleming alpha spending function, based on the actual number of events observed.

If interim comparison of OS in either all randomized subjects or randomized subjects with PD-L1 CPS  $\geq$  20 is significant, the DMC will inform the sponsor, as described in the DMC charter. If comparison of OS in the randomized subjects with PD-L1 CPS  $\geq$  20 is significant, OS in randomized subjects with PD-L1 CPS  $\geq$  1 will be subsequently tested using group sequential testing procedure. The overall alpha for this secondary endpoint will be determined following the graphical procedure which will be illustrated in Appendix 4.

